	11.1.4 Use Scenario 4: Interpret more results
•	Configuration:
Th	e study moderator provides a CO log for the participant to interpret.
>	Study moderator and/or observer to monitor participant

• Prompt 1:

What does it mean if the result of a person's breath test looks like this? (Moderator points to a green, orange, red or gray result. An attempt will be made to evenly distribute the order the colors are presented across all groups by counterbalancing. Counterbalancing scheme will be provided in the final report. Moderator will only ask about results that were not previously

covered in Scenario 3)

Expected response: See 11.1.3 response

• Prompt 2:

What does it mean if the result of a person's breath test looks like this? (Moderator points to a green, orange, red or gray result, counterbalanced across participants. Moderator will only ask about results that were not previously covered in Scenario 3)

Expected response: See 11.1.3 response

• Prompt 3:

What does it mean if the result of a person's breath test looks like this? (Moderator points to a green, orange, red or gray result, counterbalanced across participants. Moderator will only ask about results that were not previously covered in Scenario 3) Note that Prompt 3 will be asked unless all result colors were previously covered.

Expected response: See 11.1.3 response

- Prompt 4:
- Prompt 5:

Are you ready to proceed with submitting another breath sample?

• Prompt 6 (if answer no to prompt above):

Do whatever you would normally do at home. Let me know when you are ready to submit the breath sample.

- 11.1.5 Use Scenario 5: Submit a breath sample with a new straw (this breath sample will be used as part of the paired breath sample for the Performance part of the study)
- Prompt:

Please use a new straw and submit a breath sample.

- Study moderator and/or observer to monitor for lightheadedness while providing a breath sample.
- > Study moderator and/or observer to monitor and record the number of seconds of participant's breath hold starting from inhalation.
- Tasks:
 - Assemble the Carbon Monoxide Breath Sensor

- Submit a breath sample
- Study observer confirms breath sample taken 3 to 5 minutes from last Guided Breath Test breath sample, and records the time of the sample submission.
- Prompt:

How did that go for you?

(Next prompt is a Continuation from Use Scenario 3 above)

• Prompt:

Please walk me through your test result. What does this result mean?

 \triangleright

- Tasks:
- o Access the CO Log
- Understand result from the breath test

Expected response: See 11.1.3 response

11.1.6 Subjective Feedback Part 1

• Prompt:

Were there any points during this portion of the study that you experienced difficulty or had concerns about the product?

• Prompt:

Did you experience any moments of hesitation while using the product?

• Prompt:

Do you have any safety concerns regarding the product or labeling?

11.1.7 Comparative Breath Sample with the Predicate Device followed by Breath Sample to Measure Hydrogen

Note this is NOT a Use Scenario but is included here to thoroughly represent the flow of this portion of the study.

• Prompt:

Now we are going to submit a sample using another Carbon Monoxide Sensor

• Subject provides a breath sample using the predicate CO breath sensor (Bedfont), submitted

with guidance by a trained test administrator.

- > Study observer confirms breath sample taken 3 to 5 minutes after the previous breath sample (from section 11.1.5) and records the time of the sample submission.
- > The Bedfont CO breath sensor result will be documented.
- ➤ Bedfont CO breath sensor result and COBSS result will be photographed side by side with participant number.
- Prompt:

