7.4 Breath Sensor Application (Getting Started)

After pairing, the BSA displays a Getting Started screen containing a brief video tutorial on how to submit a breath sample. This video depicts the user steps to submit a breath sample, as described in the User Manual. The BSA software automatically advances to and requires the user to complete the video tutorial after pairing. The video tutorial must be completed to advance further in the set-up and use of the BSA (system requirement). The video tutorial can be paused and played again. It is also accessible to the user at any time through the Settings screen in the BSA.

Next, a Guided Breath Test (GBT) function is used by the user wherein the BSA prompts the user through the steps of submitting a breath test (interactive version of the user steps disclosed in the User Manual). Based on the user's adherence to the proper technique, the GBT provides the user with a pass or fail. Pass or fail status is communicated to the user by the CO Breath Sensor LED (flashing green indicates pass and flashing red indicates fail), as well as the screen on the BSA, which includes a smiley face, flashing green dot and descriptive text for pass, or, a sad face, flashing red dot and descriptive text for fail

The BSA software requires the user to complete three GBTs before advancing further in

The BSA software requires the user to complete three GBTs before advancing further in the set-up and use of the BSA.

The user may repeat the GBT as often as they like if additional education and reinforcement of the technique is desired. The GBT is also accessible to the user at any time through the device button in the upper left corner of the CO Log screen in the BSA.

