Once the study subject has completed the system-required set-up and self-training on the study device, they will be asked if they feel ready to proceed with submitting another breath sample (continuing to the paired breath samples). If a subject indicates they do not feel ready, they will be asked to do what they would normally do at home to prepare to use the product and to let the test administrator know when they are ready to submit another sample.

When the subject indicates readiness to provide a breath sample, he/she will be instructed to proceed to provide one breath sample using the study device. After providing this breath sample, the subject will be asked to interpret his/her breath sample result followed by the first set of subjective questions.

Within 3-5-minutes of the first breath sample and after completing the questions addressing interpretation of breath sample results and the 1st set of subjective questions, a health care professional (or test administrator) will guide subject through the submission of the second breath sample of the paired breath sample using the predicate device.

[figure not shown]
CO levels decrease gradually in the breath with time (half-life 4-5 hours), so it is not expected that the second sample in each paired sample will be substantially lower than the first sample.

A third breath sample to measure hydrogen (Gastro+ Gastrolyzer ®, Bedfont Scientific Ltd.) will be completed .

Upon completion of the paired breath sample and hydrogen breath sample, subjects complete the 2^{nd} set of subjective questions and then do the user documentation assessment. During this time, ease of use and clarity of content are assessed for the product labeling, with focus on the User Manual. This is followed by rating scales.

26

Figure 7. Study session flow

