11.0 TECHNICAL APPROACH AND STUDY DESIGN

Each study session will have the following format:

- 1. Introduction
- Simulated Use
- 3. Performance Paired Breath Samples (performed during Use Scenarios; see section 11.1)
- 4. User Documentation Assessment
- 5. Subjective Feedback and Rating Scales

Following a brief introduction session, each participant will undergo a study session lasting about 90 minutes. The study session will comprise 8 individual use scenarios, comparative performance paired breath samples with the study device and predicate device, user documentation (User Manual, Quick Start Guide, and Reference Card) assessment, subjective feedback and rating scales. In addition to the subjective feedback obtained during the defined sections below, subjective feedback may be collected during the use scenarios and User Documentation assessment to inform root cause analysis.

The use scenarios included in the study consider inputs from risk management documentation (COBSS Use FMEA, to test mitigations to device use (operation) related hazards. Each use scenario is expected to take up to 5 minutes (most will take 2-3 minutes). The use scenarios are listed in Table 2.

The study session will be conducted as a simulated use study where each participant will have access to the study article, a smartphone of their choice (Apple Inc. iPhone or Android smartphone), and will be monitored while performing the use scenarios. Each use scenario is monitored for difficulties, close calls and use errors. The use scenarios will allow for a detailed and focused assessment of the different components of the COBSS set-up and use.

Table 2 . Use Scenarios for Usability Validation

ID	Use Scenarios
1	
2	
3	
4	
5	
6	
7	
8	

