11.1.2 Use Scenario 2: Start-up device and complete self-training

• Configuration:

The study moderator presents the participant with the Carbon Monoxide Breath Sensor device package and the smartphone of user's choice.

Prompt:

Imagine you just bought this from the store. Given that you just bought this product, you can take as much time as you need to familiarize yourself with the product. Please start using the product when you are ready.

(If user does not begin using device after familiarization period) Please proceed with using the product.

	ERFORMANCE, HUMAN FACTORS, AND USABILITY STUDY FROTOCOL
• Tasks:	
0	Open the Carbon Monoxide Breath Sensor packaging and remove contents
0	Open the installed BSA on the smartphone
0	Pair Breath Sensor with the smartphone
0	Complete tutorial
0	Complete
• Prompt:	
How did that	go for you?
11.1.3 Use	e Scenario 3: Interpret your results – Part 1
• Prompt:	
Please walk n	ne through your test results. What does each result mean?
>	
• Tasks:	
0	Access the CO Log
0	Understand results from the breath tests
Note: This Us section 11.1.5	se Scenario will be continued for interpreting results for Use Scenario 5. (See below.)
Expected Res	ponse:
For green value	ue:
•	
Or,	
•	
Or,	
•	
For orange va	lue
TOTOTALISE VA	uuc.

	Or,
•	
	Or,
•	
Fo	r red value:
•	
	Or,
•	
	Or,
•	
Fo	r grey bar (no value is provided in this instance):
•	
	Or,
•	
	Or,
•	

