12.2.2 Performance

See Sections 9.4 and 9.5 for statistical methodology. A paired breath sample is defined as subject submitting a breath sample unassisted using the study device, waiting 3-5 minutes, and submitting a breath sample assisted by a health care professional (or test administrator) using the predicate device.

A final report will be created to capture the results and analyses of the findings.

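### Does the 3-to-5-minute check after the last Guided Breath Test put the performance comparison at risk, given the steps that come before the sample?

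*Combined protocol and SAP*

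**What the plan says.** Section 11.1.5 (Use Scenario 5) covers the COBSS sample that becomes the first half of the performance pair. It includes an observer check: "Study observer confirms breath sample taken 3 to 5 minutes from last Guided Breath Test breath sample". The observer also records the time of submission.

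The required Guided Breath Tests belong to set-up. Section 7.4 states: "The BSA software requires the user to complete three GBTs before advancing further in" the set-up and use of the app. That places them in Scenario 2. This is inferred from Sections 7.4 and 10.0, because the last task listed for Scenario 2 is cut off in the public text.

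Three things then come before the sample:

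- **Scenario 3 Part 1 (Section 11.1.3).** The subject interprets the results so far ("What does each result mean"). A note adds that this "Scenario will be continued for interpreting results for Use Scenario 5", and Section 11.1.5 puts that continuation after the sample.
- **Scenario 4 (Section 11.1.4).** The moderator asks only about result colours that Scenario 3 did not cover.
- **Readiness.** A subject who is not ready is told: "Do whatever you would normally do at home. Let me know when you are ready to submit the breath sample". Section 10.0 says the same: "they will be asked to do what they would normally do at home to prepare to use the product". Neither gives a time limit.

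On durations, Section 11.0 says: "Each use scenario is expected to take up to 5 minutes (most will take 2-3 minutes").

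Section 12.2.2 defines the pair as an unassisted COBSS sample, then "waiting 3-5 minutes, and submitting a breath sample assisted by a health care professional (or test administrator") on the predicate device. Neither Section 10.0 nor Section 12.2.2 mentions an interval from the Guided Breath Test.

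**The concern.** The upper limit of 5 minutes seems to clash with the sequence it governs. Two scenarios at the typical 2-3 minutes each take 4-6 minutes, and 10 at the stated maximum. That is before the readiness step, a new straw and the sample itself.

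If staff enforced the limit, they might hurry subjects through the comprehension questions and the readiness step, which would affect the usability findings and the unassisted sample. If they did not, many of the 70 performance samples might carry a deviation. Section 11.1.5 does not say what follows from a miss, so one could fear that pairs would be kept or dropped once both readings were known. Section 12.2.2 omits this window, so the sections also seem to differ on what a valid sample requires.

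**Working it through.** The plan gives no figure for the interval from Guided Breath Test to sample, or for the share of subjects inside it, so there is no figure to reproduce.

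**Inputs**

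- Window: 3 to 5 minutes (Section 11.1.5).
- Scenario time: 2-3 minutes for most, up to 5 (Section 11.0).
- Sample step (Section 7.5): button about 2 s, breath hold about 10 s, exhalation 6-12 s.
- CO half-life: 4-5 hours (Section 10.0).

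**Step 1: range of elapsed time.** The sample step takes (2 + 10 + 6)/60 = 0.3 to (2 + 10 + 12)/60 = 0.4 minutes. With two full scenarios at 2-3 minutes, the interval runs from 2 + 2 + 0.3 = 4.3 minutes, which is inside the window, to 3 + 3 + 0.4 = 6.4 minutes, which is outside. At the maximum, 5 + 5 = 10 minutes.

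**Step 2: share late if both scenarios count in full.** Assume independent durations, uniform on 2-3 minutes, plus e minutes for everything else (e between 0 and 1). Then P(late) = 1 - (1 - e)²/2.

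| e (min) | Late |
|---|---|
| 0 | 50% |
| 0.3 | 75.5% |
| 0.5 | 87.5% |
| 1 | 100% |

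**Step 3: share late if only part of Scenario 3 precedes the sample.** Let f be the fraction of Scenario 3 done beforehand. The plan does not give f. The sample is late when f·A + B + e > 5, with A and B uniform on 2-3 minutes.

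| f | e = 0.3 | e = 0.5 | e = 1 | e = 2 |
|---|---|---|---|---|
| 0.50 | 0% | 0% | 25% | 100% |
| 0.67 | 7% | 19% | 67.5% | 100% |
| 0.75 | 20% | 37.5% | 83% | 100% |

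For example, with f = 0.5 and e = 0.5 the longest interval is 0.5 × 3 + 3 + 0.5 = 5.0 minutes, so nobody is late. The uniform distribution, f and e are all assumptions. The durations in Section 11.0 describe the eight scenarios in general, not these two, and not a spread over subjects.

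**Step 4: what restarts the clock.** The window runs from the last Guided Breath Test. Sections 7.4 and 7.9 let the subject repeat that test at any time. A subject who practises again during the readiness step starts a new interval, so the untimed step does not by itself make the window unattainable.

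**Step 5: effect of a miss on the endpoint.** The fraction of CO lost in t minutes with half-life h minutes is 1 - 2^(-t/h).

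- t = 5, h = 240 (4 hours): 1 - 2^(-5/240) = 1.4%.
- t = 5, h = 300 (5 hours): 1 - 2^(-5/300) = 1.1%.

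The loss comes before both samples. It scales a subject's two true CO levels by the same factor and leaves their ratio unchanged. The 3-5 minutes allowed between the devices cost 1 - 2^(-3/300) = 0.7% to 1 - 2^(-5/240) = 1.4%. That loss does fall on one device only, and Section 10.0 already judges it not substantial.

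**Step 6: status of a pair after a miss.** Section 11.1.5 describes an observer check and attaches no validity condition to it. Section 12.2.2 gives the definition of a pair, and the Guided Breath Test is not part of it. A pair with a missed check but a correct interval between devices therefore meets the definition. Section 12.4 has all deviations identified, recorded and analysed in the final report.

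**The case for a change.** The strongest opposing case is that the mitigating features are weaker than they look. Scenario 3 Part 1 asks about several results and its continuation about only one, so most of Scenario 3 probably comes before the sample. Readings minutes apart will usually share a colour, so Scenario 4 is often barely shortened. A subject who repeats the test and is ready at once could breach the 3-minute lower limit instead. Section 12.4 leaves deviations to consensus in a study team of sponsor employees and consultants, and Section 11.1.7 has the two readings photographed side by side. A minimum interval and an explicit no-exclusion rule would then cost only a few words.

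Much of this stands as description. The window is hard to meet and may often be missed, on either side, and Section 11.1.5 does not say how a miss is handled.

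The consequences do not follow. Section 11.5 requires tasks to be done independently and naturally, without coaching, so hurrying subjects would go against the plan. Discretion over pairs is limited by the definition in Section 12.2.2. That section refers to Sections 9.4 and 9.5 for the statistical methods, and these are heavily redacted, so the absence of a further rule cannot be asserted. The suggested rewrite would also remove an upper limit whose purpose the visible text does not state.

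**Conclusion.** No change is needed. The timing tension is real: Section 11.1.5 sets a check that the preceding steps make hard to satisfy, and that fails if both scenarios run to 5 minutes. It is a clumsy operational check on which Sections 10.0 and 12.2.2 are silent. It does not alter the definition of a valid pair.

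How many subjects miss it is unknown. Under the assumptions shown, the share runs from 0% to 100%, so a claim that most do is not supported. A 5-minute overrun costs about 1.1-1.4% of CO, shared by both devices, which is negligible for a correlation across smokers whose intake ranges from 2 to 16 or more cigarettes a day. This rests on the plan's half-life and on the interval between devices being held as Sections 11.1.7 and 12.2.2 require. It also assumes that the longer rest affects the COBSS reading only through CO decline; the documents give no sign of another effect.

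An analyst would follow Section 12.2.2, keep every pair that meets it and report missed checks as deviations. The time of the COBSS sample is recorded in any case. Rewriting the window would change no result.

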11.1.8 Use Scenario 6: Charge the Carbon Monoxide Breath Sensor

Prompt:

Please proceed to charge the Carbon Monoxide breath sensor.

- Tasks:
- Connect the micro-USB cable
- o Charge the device

11.1.9 Use Scenario 7: Set reminders for future breath tests

• Prompt:

Please set reminders to perform breath tests every 2 hours from 8am to 10pm.

- Tasks:
- o Access the BSA Settings Page
- Set time limits and frequency for reminders

11.1.10 Use Scenario 8: Access the Frequently Asked Questions Page in the Application

• Prompt:

Please access the Carbon Monoxide Breath Sensor Frequently Asked Questions page in the application.

- Tasks:
- Press Setting button
- o Press Frequently Asked Questions on Screen

11.1.11 Subjective Feedback Part 2

•	Prompt:		
•			

Upon completion of the use scenarios and comparative performance paired breath samples, a user documentation assessment session and a subjective feedback session will be conducted to better inform the safety and efficacy of the COBSS.

11.2 USER DOCUMENTATION ASSESSMENT

Participants will never be asked to refer to the User Manual, Quick Start Guide, or Reference Card during simulated use scenarios. Any instance of participants referring to the instructions in the User Manual, Quick Start Guide, or Reference Card during the simulated use scenarios will be recorded and assessed.

After completion of the use scenarios and comparative performance paired breath samples, the user documentation (User Manual, Quick Start Guide, and Reference Card) will be tested for ease of use and clarity of content. Each user documentation assessment session will have test cases to assess the findability and the interpretation of knowledge task data found in the User Documentation. Participants will be asked to find and/or interpret 12 pieces of essential information. Participants will demonstrate understanding through verbal explanation. The questions and answers for the user documentation assessment are found in Table 3.

Table 3. Knowledge Tasks for User Documentation Assessment

Knowledge Task ID	Knowledge Tasks	Question	Participant Response
KT 1			

KT 2		
KT 3		

	V	
KT 4		
KT 5		

Prompt: Please read to opened up).	hese pages (Provide Use I am going to ask you so	er Manual with the Warnings, It	Precautions, Notes pages s.
KT 6			
			•
KT 7			
).	
KT 8			

KT 9		
KT 10		
KT 11		
KT 11.1 (Ask only if participant did not state both		

expected answers)		
KT 12		

11.3 SUBJECTIVE FEEDBACK AND RATING SCALES

In addition to the subjective feedback obtained periodically throughout the study session, subjective feedback may be collected during the use scenarios and user documentation assessment to inform root cause analysis. Following the user documentation assessment, the participants will be subjected to rating scale questions to rate the ease of use of the device, the clarity of the user documentation and their ability to understand and interpret the test results.

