2.2 STUDY RATIONALE

and, will assess the human factors and usability of the COBSS.

Performance: We aim to non-invasively measure carbon monoxide (CO) levels in the exhaled breath of study subjects using two different types of measurement devices. We will assess the correlation between the measured CO levels (in ppm) of the study CO breath sensor (COBSS; Carrot Sense) completed by a lay user with no personal instruction (using labeling only) and the predicate CO breath sensor (Micro+Smokelyzer; Bedfont) administered by a person trained to instruct users on submitting a sample with the device.

Human Factors and Usability: We aim to assess whether an untrained lay user group (representative of intended users) can operate the device and interpret the results correctly using only the instructions that will be provided with the marketed device.

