9.2 STUDY ENDPOINTS

9.2.1 Human Factors

Assessment of intended user performance in use scenarios, user documentation assessment, subjective feedback and rating scales.

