9.8 USER MANUAL AND TRAINING

The COBSS was designed to be as intuitive as possible, such that users are able to understand how to use the product on their own. No in-person training is formally offered to COBSS users. However, the User Manual, Quick Start Guide and Reference Card are included with the purchase of the device. Additionally, users are required by the COBSS software design to complete the COBSS video tutorial and 3 Guided Breath Tests. The video tutorial and Guided Breath Test provide in-app user training and reinforce the procedure of submitting a CO breath sample using the device.

Since in-person training will not be formally offered to all users who purchase the COBSS, inperson training will not be included in this study. Study participants will have access to the User Manual, Quick Start Guide and Reference Card in the device package, as will be the case for the marketed product. Any instance of participants referring to the User Manual, Quick Start Guide or Reference Card during the study will be recorded.

Additionally, the video tutorial and Guided Breath Test, offered by the COBSS user interface, as part of BSA start up, will help participants familiarize themselves with the device and understand how to use it. The BSA software requires completion of both the video tutorial and 3 Guided Breath Tests to advance through the COBSS set-up and start using the device.

During the usability validation, the participants will have the User Manual, Quick Start Guide, Reference Card, video tutorial and Guided Breath Test available to them at any point during the study. This mimics real-world use. However, they will not be asked to read instructions (except during the knowledge questions covered in the User Documentation Assessment – see Section 11.2) or use any of the forms of training available. At the beginning of the study, participants will have the opportunity to familiarize themselves with the product and instructions.

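### Device ease-of-use and result-interpretation ratings are, as far as the visible text shows, taken only after the directed documentation assessment, so they reflect prompted rather than voluntary reading of the labeling (minor)

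*Combined protocol and SAP*

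**What the plan says.** Section 9.2.1 defines the human factors endpoint as "Assessment of intended user performance in use scenarios, user documentation assessment, subjective feedback and rating scales". Rating scales are thus one of its four named parts.

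Section 11.3 fixes when the ratings are taken: "Following the user documentation assessment, the participants will be subjected to rating scale questions to rate the ease of use of the device". It then adds two further attributes to the same block, the clarity of the user documentation and "their ability to understand and interpret the test results". Section 10.0 gives the same order: it describes the documentation assessment, in which "ease of use and clarity of content are assessed for the product labeling, with focus on the User Manual", and continues "This is followed by rating scales". The numbered session format in Section 11.0 also puts the documentation assessment fourth and the rating scales fifth.

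On content, Section 11.2 states: "Participants will be asked to find and/or interpret 12 pieces of essential information". Part way through Table 3, after KT 5, a prompt asks the subject to read the Warnings, Precautions and Notes pages of a User Manual handed over already open.

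On prompted reading in general, Section 9.8 says that participants have all the materials at hand but "they will not be asked to read instructions (except during the knowledge questions covered in the User Documentation Assessment".

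**The concern.** The protocol separates two ways of meeting the labeling. During simulated use, subjects consult it if and when they choose, as a purchaser would. During the documentation assessment they are sent to it and questioned on it. Sections 9.8 and 11.2 protect the use scenarios from the second kind of exposure. The ratings of device ease of use and of result interpretation do not get that protection, although both concern the experience that the use scenarios are meant to create.

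The study question in Section 2.2 is: "We aim to assess whether an untrained lay user group (representative of intended users) can operate the device and interpret the results correctly". The sentence goes on to limit the user to the instructions that come with the marketed product. Ratings offered in support of that question should describe use with the labeling consulted as the user chooses. A subject who never opened the manual during the scenarios will have worked through parts of it before scoring how easy the device was and how well the results were understood. The User Manual is also the source of the color key to CO results (Figure 3) and one of the sources of the breath-sample steps (Section 7.5), so the material is relevant to what is rated. At stake is how two sets of scores may be described in the final report.

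**Working it through.** No formula applies. The point concerns the order of assessments and depends on no alpha, power, effect size or sample size. The 70 subjects come from the power calculation for the device correlation and enter here only as the number affected. The check is to set the session order beside the rule on prompted reading.

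**Session order (Sections 10.0, 11.0 to 11.3)**

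| Step | Content | Prompted to read the labeling? |
|---|---|---|
| Use Scenarios 1 to 5 | Self-selection, set-up and self-training, interpreting own and sample results, breath sample | No |
| Subjective Feedback Part 1 (11.1.6) | Three open questions on difficulty, hesitation and safety | No |
| Predicate and hydrogen samples (11.1.7) | Predicate sample guided by a test administrator | No COBSS reading described |
| Use Scenarios 6 to 8 | Charging, reminders, FAQ page | No |
| Subjective Feedback Part 2 (11.1.11) | Prompt blacked out | Not visible |
| Documentation assessment (11.2) | 12 knowledge tasks, reading prompt after KT 5 | **Yes** |
| Rating scales (11.3) | Device ease of use, documentation clarity, result interpretation | Follows the prompted reading |

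**Which ratings need the exercise first?**

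- Documentation clarity: yes. It cannot sensibly be rated before the documents have been worked through.
- Device ease of use: no. Its object is the device, and the last device task is Use Scenario 8.
- Ability to interpret results: no. The subject has interpreted results in Use Scenarios 3, 4 and 5.

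So 3 rated attributes − 1 that needs the exercise = 2 that are placed after it without need.

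**Is there an earlier rating to compare with?** None is visible. Subjective Feedback Part 1 is open-ended and has no scale. The content of Part 2 cannot be checked.

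**Could the analysis separate the effect?** Every subject follows the same order. With no rating before the exercise and no group rated without it, the data contain no contrast from which carry-over could be estimated or removed.

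**What precedes the exercise and is untouched?** Observed performance in all 8 use scenarios, the interpretation tasks in Use Scenarios 3 to 5, and the open feedback in Part 1. Section 11.4 lets the Use FMEA govern acceptance, and no threshold on the ratings is stated.

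**The case against.** The strongest reply is that the order does little harm, and much of that reply stands.

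- **The labeling belongs to the product.** A reader might infer that the ratings come from instructed users instead of the untrained users in the study question. Section 2.2 does not support that. It allows the marketed instructions, the exercise uses only those, no in-person COBSS training is given, and every subject has already had to complete the video tutorial and three Guided Breath Tests. The real contrast is prompted against voluntary reading.
- **The moderator does not teach.** In Section 11.2 the subject finds the information and explains it aloud, and Section 11.5 bars coaching. It would be wrong to say that the manual is explained to the subject.
- **Direction is unknown.** A reader might expect inflated scores. The knowledge-task wording is blacked out, so it is not known which items touch on operation or results. A frustrating search or a page of warnings could equally lower the scores.
- **An earlier rating may exist.** The Part 2 prompt is blacked out. One can say only that no earlier rating is visible.
- **Reordering does not give a pristine rating.** The two items would still follow the guided predicate sample and the moderator's questions about result colors in Use Scenarios 3 to 5. The change removes the influence of prompted reading and no other.

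What the reply does not supply is a reason for these two ratings to follow the exercise. The protocol states none, and its own rule in Section 9.8 treats prompted reading as something to keep away from simulated use.

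**Conclusion.** The point holds in a limited form. As far as the visible text shows, two of the three attributes in the rating-scale part of the human factors endpoint are recorded only after prompted reading of the labeling, in all 70 planned subjects. The scores cannot later be separated from that exercise.

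A reader might go further and infer that the study cannot show whether lay users can operate the device and interpret its results. The documents do not support this. That conclusion rests on observed tasks completed before the exercise and on risk acceptability under the Use FMEA. The protocol nowhere says that the ratings alone will carry it. They are supportive subjective data.

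Two assumptions remain. The first is that the blacked-out Part 2 prompt does not already contain these ratings; if it does, the point falls away. The second is that the prompted reading can influence what is rated. This is plausible from the manual's content, but the documents do not demonstrate it or give a size. Severity: minor.

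**What to change.** Split the rating block. Ask the device ease-of-use and result-interpretation items directly after Use Scenario 8 and Subjective Feedback Part 2 (Section 11.1.11), before the documentation assessment in Section 11.2 begins. Keep only the documentation-clarity item after Section 11.2. Align the order in Sections 10.0, 11.0 and 11.3 and in Figure 7.

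If the sponsor keeps the present order, the final report should label these two as post-documentation ratings and should not present them as ratings of undirected use.

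The cost is a reordered data sheet and moderator script. No question or staff is added, and essentially no session time.
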